2.5.1.5 Dose reductions, interruptions, or permanent discontinuations

The number of patients who have dose reductions or interruptions, and the reasons, will be summarized separately for each of the study treatment components.

‘Dose interrupted’ and ‘Dose changed’ fields from the Dosage Administration CRF pages (DAR) will be used to determine the dose interruptions and dose changes, respectively.

Dose reduction: a dose change where the prescribed dose level is lower than the previous prescribed dose level or where the actual dose administered is lower than the prescribed dose. Only dose change is collected in the CRF, number of reductions will be derived programmatically based on dose change flag and the change and the direction of the change. Dose reduction will be reported for VAY736 only.

Dose interruption: Actual dose administered equal to zero, between the first and last non-zero doses, following a non-zero actual dose administered. Dose interruption is collected as such in the treatment page eCRF. Number of dose interruptions and corresponding reason will be summarized.

- For VAY736, ‘Dose interrupted’ field from the Dosage Administration CRF pages (DAR) will be used to determine the dose interruptions.
- For ibrutinib, dose interruptions will be captured in the dose change log.

The corresponding fields ‘Reason for dose change/dose interrupted’ will be used to summarize the reasons. For the purpose of summarizing interruptions and reasons, in case multiple entries for interruption that are entered on consecutive doses with different reasons, they will be counted as separate interruptions. However, if the reason is the same in these mentioned multiple entries on consecutive doses, then it will be counted as one interruption.

2.5.2 Prior, concomitant and post therapies

Concomitant therapies are defined as any medications (excluding study treatment, prior antineoplastic treatments) and significant non-drug therapies (including physical therapy and

blood transfusions) administered in the study and are recorded in the Concomitant Medications and Prior or Concomitant non-drug therapies/procedures eCRF. These therapies will be coded using the WHO Drug Reference Listing (WHO DRL) dictionary that employs the WHO Anatomical Therapeutic Chemical (WHO ATC) classification system. Significant non-drug therapies will use MedDRA coding.

Any concomitant therapies starting prior to or after the start of study treatment will be listed.

A separate listing will be provided for instances of concomitant, limited-field palliative radiotherapy to non-target lesion(s). Per protocol VAY736Y2102-CSP-Section 6.4, such concomitant therapies are allowed, and will be recorded on the Concomitant radiotherapy/surgery case report form (CRF) page.

The imputation of a concomitant medication start date will follow the same conventions as for an AE start date (see [Section 2.8.2.1.1](#) for AE date imputation rules). No imputation will be performed for concomitant medication end dates.

2.5.3 Compliance

Compliance to the study treatment will be summarized in terms of the RDI. The predefined RDI categories are < 0.5 , $\geq 0.5 - < 0.75$, $\geq 0.75 - < 0.9$, $\geq 0.9 - < 1.1$ and ≥ 1.1 . The number and proportion of patients falling in each category will be presented.

2.6 Analysis of the primary objective

The primary objective is to characterize the safety and tolerability of the combination of VAY736 with ibrutinib, and to determine the MTD or RDE for the combination.

The following primary endpoints are of interest in both the dose-escalation and dose-expansion parts of the study.

- Incidence and severity of adverse events (AEs) and serious adverse events (SAEs)
- Changes in laboratory parameters and vital signs
- Dose interruptions, reductions, and dose intensity

The dose-escalation part will study an additional endpoint:

- Incidence of DLTs during the first treatment cycle of the investigational treatment.

For the analysis of safety and tolerability endpoints see VAY736Y2102-CSP-Section 10.5.3, in addition to analysis of the DLT rate as below.

2.6.1 Reports of DLT analysis

A dose-limiting toxicity (DLT) is defined as a clinically relevant adverse event or abnormal laboratory value or dose reduction due to AE which occur ≤ 28 days following the first administration of study treatment as defined in VAY736Y2102-CSP-Section 6.2.4, Table 6-3.

The MTD (or RD) will be estimated in the dose-escalation part of the study by modeling the probability of DLT occurrence in Cycle 1 for patients in the dose-determining set (DDS). This probability is estimated by the statistical models in [Section 2.6.1.1](#).

The following reports will be produced based on the dose determining set:

- A plot of posterior interval probabilities will be presented in the body of the CSR;
- Summary of the DLTs with onset during the evaluation period (dose escalation part only) by primary system organ class, preferred term: recommendations at the time of database lock will be included in the body of the CSR. Summaries of recommendations from each dose escalation meeting (DEM) will be included in Appendix 16.1.9 of the CSR;
- Listing of inferential results from the BLRM at the time of database lock, will be included in Appendix 16.1.9.

The Bayesian model for DLT rates is described in the next section.

2.6.1.1 Statistical hypothesis, model, and method of analysis

Identification of a recommended dose

Estimation of the MTD of the treatment will be based upon the estimation of the probability of DLT in cycle 1 for patients in the DDS. A recommended dose below the MTD may be identified based on other safety, clinical, PK, and PD data (see VAY736Y2102-CSP-Section 6.2.3).

Bayesian adaptive approach

The dose escalation part of this study will be guided by a Bayesian analysis of Cycle 1 dose limiting toxicity (DLT) data for VAY736 and ibrutinib. The Bayesian analysis will be based on a model with three parts, representing:

- Single agent VAY736 toxicity
- Single agent ibrutinib toxicity
- Interaction

The single-agent toxicities are modeled as follows. Let $\pi_1(d_1)$ be the risk of DLT of the first cycle for VAY736 given as a single agent at total cycle 1 dose d_1 (Q2W VAY736 dose mg/kg * 2); $\pi_2(d_2)$ be the risk of DLT of the first cycle for ibrutinib given as a single agent at daily dose d_2 (mg). These single agent dose-DLT models are logistic:

$$\text{VAY736: } \text{logit}(\pi_1(d_1)) = \log(\alpha_1) + \beta_1 \log(d_1/d_1^*) \quad (1)$$

$$\text{Ibrutinib: } \text{logit}(\pi_2(d_2)) = \log(\alpha_2) + \beta_2 \log(d_2/d_2^*) \quad (2)$$

where $d_1^* = 3.0$ mg/kg total cycle 1 dose (1.5mg/kg * 2) and $d_2^* = 420$ mg daily are used to scale the doses of VAY736 and ibrutinib, respectively. Hence, α_1 and $\alpha_2 (>0)$ are the single-agent odds of a DLT of the cycle 1 at 3.0 mg/kg total cycle 1 dose and 420 mg daily, respectively; and β_1 and $\beta_2 (>0)$ are the increase in the log-odds of a DLT by a unit increase in log-dose.

Under no interaction, the risk of a DLT at dose d_1 of VAY736 and dose d_2 of ibrutinib is:

$$\pi_{12}^0(d_1, d_2) = 1 - (1 - \pi_1(d_1))(1 - \pi_2(d_2))$$

To allow for interaction between VAY736 and dose d_2 of ibrutinib, an odds multiplier is introduced. The risk of DLT for combination dose (d_1, d_2) is then given by:

$$\text{odds}(\pi_{12}(d_1, d_2)) = \exp(\eta \times d_1/d_1^* \times d_2/d_2^*) \times \text{odds}(\pi_{12}^0(d_1, d_2))$$

where $\text{odds}(\pi) = \pi/(1 - \pi)$; and η is the log-odds ratio between the interaction and no interaction model at the reference doses. i.e., 3.0 mg/kg(1.5 mg/kg * 2) of total cycle 1 VAY736 and 420 mg of daily ibrutinib. Here $\eta = 0$ corresponds to no interaction, with $\eta > 0$ and $\eta < 0$ representing synergistic and antagonistic toxicity, respectively.

Specifications of the prior distributions for $\alpha_1, \alpha_2, \beta_1, \beta_2$, and η are given in VAY736Y2102-CSP-Section 14.2.2.

Assessment of patient risk

After each cohort of patients, the posterior distribution for the risk of DLT for new patients at combination doses of interest will be evaluated. The posterior distributions will be summarized to provide the posterior probability that the risk of DLT lies within the following intervals:

Under-dosing:	[0 , 0.16)
Targeted toxicity:	[0.16 , 0.33)
Excessive toxicity:	[0.33 , 1]

The escalation with overdose control (EWOC) principle

Dosing decisions are guided by the escalation with overdose control principle ([Rogatko et al 2007](#)). A combination dose may only be used for newly enrolled patients if the risk of excessive toxicity at that combination dose is less than 25%.

Dose recommendations

At each dose-escalation meeting, summaries of the posterior distribution of DLT rate will be listed for each dose. In particular, the posterior probabilities of the three toxicity intervals will be listed for each provisional dose level. Complete guidelines for dose-escalation decision making are given in VAY736Y2102-CSP-Section 6.2.3.

Change in dose schedule

In the case that additional dosing schedules for VAY736Y are explored during dose-escalation, a BLRM of the same functional form will be used to estimate the dose-DLT relationship for each new schedule. Data from previous or concurrently explored schedules will be used to inform the dose escalation for the new schedule. At each time the decision is taken to explore a new schedule, the model to be used to guide escalation in that schedule will be constructed. The model will be finalized prior to first patient treated under the new schedule and will be documented in full in CSR Section 16.1.9. The details may refer to VAY736Y2102-CSP-Section 14.2.

In addition, in case VAY736Y Q2W dosing schedule continues, and a new dosing schedule is explored during dose-escalation, a BLRM of the same functional form described in VAY736Y2102-CSP-Section 14.2 will be used to estimate the dose-DLT relationship for each schedule based on a newly derived prior incorporating the historical trial data and the on-study data from previous schedule.

2.6.2 Handling of missing values/censoring/discontinuations

The reason for discontinuation from study will be summarized and listed, along with dates of first and last study drug treatment, duration of exposure to study drug treatment and date of discontinuation for each patient.

Other missing data will simply be noted as missing on appropriate tables/listings.

Patients with unknown or missing response and who are treated in the study but provide no information on response at the end of treatment will be treated as non-responders and will be included in the denominator when calculating CR/CRi rate or ORR.

2.6.3 Supportive and sensitivity analyses

Additional [REDACTED] supportive analyses will be conducted, if appropriate, [REDACTED]
[REDACTED]

2.7 Analysis of the key secondary objective

Not applicable.

2.8 Analysis of other secondary objective(s)

2.8.1 Efficacy analysis

Evaluation of anti-tumor activity will be based on investigators' assessment per IWCLL criteria (see VAY736Y2102-CSP-Appendix 1 for details) as documented in the eCRF. The variables used to evaluate anti-tumor activity are CR/CRi rate, clearance of ibrutinib resistance mutations, overall response rate (ORR), and time to progression (TTP). Analyses of these variables will use the FAS, including patients from both the escalation and expansion parts. All analyses will be provided by dose level in dose escalation and by two arms in dose expansion.

Rate of CR/CRi at C9 for expansion arm A and arm B: The proportion of patients with CR or CRi assessed by investigators per IWCLL criteria (see VAY736Y2102-CSP-Appendix 1 for details) at C9 will be provided. The rate of CR/CRi at C9 is the primary endpoint for the evaluation of anti-tumor activity and will be analyzed for each expansion arm using a Bayesian modeling approach.

A minimally informative beta distribution is used as prior distribution with parameters $a=0.25$ and $b=1$. This assumes, *a priori*, that the response rate is 20%.

Posterior summaries for CR/CRi rate (posterior mean, including 90% credible intervals and the posterior probability that the true CR/CRi rate falls in the activity intervals defined below) will be provided:

Posterior probability of response rate intervals:

- [0, 20%] – clinically not meaningful
- [20%, 40%] – moderate clinical benefit
- [40%, 100%] – superior clinical benefit

In addition, exact confidence interval (90% CI) also will be provided.

To determine which response assessments occurred at C9, response assessment dates within a window of +/- 3 days of patient's Cycle 9 visit start date or end date will be considered as C9 responses.

Clearance of ibrutinib resistance mutation for expansion arm B is defined as less than 1% mutation bearing alleles (BTKC481 and/or PCL γ 2) during treatment (up to C9). The proportion of patients with negative mutation, where negative mutation is defined as having clearance of the baseline ibrutinib resistance mutation, will be provided along with corresponding 90% exact confidence interval (CI). Note that only R665, S707, A708 and L845 variants will be considered as functional PLC γ 2 mutations. Other PLC γ 2 variants will not be considered for this analysis.

Overall response rate (ORR) is defined as the proportion of patients with best overall response (BOR) of complete response (CR), complete response with incomplete marrow recovery (CRI), or partial response (PR), as assessed by investigators per IWCLL criteria (see VAY736Y2102-CSP-Appendix 1 for details) and will be calculated based on all response evaluations. The ORR will be calculated by dose level in dose escalation and by arm in dose expansion, and overall, and will be presented along with corresponding 90% exact confidence intervals (CI). Assessments taken after the start of alternative cancer therapy will be excluded.

Time to progression (TTP) is the time from start of treatment to the date of event which is defined as the first documented progression (defined as overall disease response assessment of PD) or death due to underlying cancer. If a patient has not had an event, time to progression is censored at the date of last adequate disease assessment. Assessments taken after the start of alternative cancer therapy will be excluded.

Median TTP (in months) with corresponding 95% CI, 25th and 75th percentiles (Brookmeyer and Crowley 1982, Klein and Moeschberger 1997) and Kaplan-Meier estimated probabilities (TTP rate) with corresponding 95% CIs (Greenwood's formula, Kalbfleisch and Prentice 1980) at several time points (3, 6, 12, 18 and 24 months) will be presented. The number (%) of progressions, deaths and patients censored will also be summarized.

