Population	Adults with CLL who have been receiving ibrutinib following relapse on another approved therapy and either have not had a complete response after 1 year of treatment or have developed a resistance mutation to ibrutinib without clinical relapse at any time during treatment. The dose expansion part of the study will also include patients who have received ibrutinib either alone or in combination (or have received ibrutinib continuously with multiple sequential combination partners) as first-line therapy and have either failed to achieve a complete response after 1 year of therapy or have developed a resistance mutation to ibrutinib.
Inclusion criteria	Written informed consent Ibrutinib dose Escalation: Patients must be receiving 420 mg ibrutinib Expansion: Patients may be on a dose of ibrutinib lower than 420 mg. Any dose must have been stable for 2 months prior to the start of study treatment. Diagnosis of CLL as per World Health Organization (WHO) classification Lack of a complete response after receiving ibrutinib for > 1 year OR presence of known ibrutinib resistance mutation Platelets $\geq 25 \times 10^9/L$ without transfusion support within 7 days of the first dose of VAY736 Eastern Cooperative Oncology Group (ECOG) performance status of 0-2

Exclusion criteria	Receipt of live vaccine within 4 weeks of starting VAY736 Known history of HIV Active hepatitis B or C infection
Investigational and reference therapy	VAY736 Ibrutinib
Efficacy assessments	Rate of patients with CR (complete response) as assessed by investigators per IWCLL at cycle 9 day 1 Overall response rate (ORR) assessed by investigators per IWCLL criteria and Time To Progression (TTP) Clearance of ibrutinib resistance mutations (BTKC481 and/or PLCy2 hotspot), defined as less than 1% mutation bearing alleles (Arm B only). [REDACTED]
Safety assessments	Safety Escalation only: Incidence of DLTs in cycle 1 (28 days) Escalation and expansion: Incidence and severity of AEs and SAEs, including changes in laboratory parameters and vital signs Tolerability Dose interruptions, reductions, and dose intensity
Other assessments	Plasma concentrations of VAY736 and ibrutinib and derived parameters Presence of anti-VAY736 antibodies [REDACTED] [REDACTED] [REDACTED]

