2.1 Study rationale and purpose

[REDACTED]

Ibrutinib has become the standard treatment for many advanced CLL patients. Although most patients benefit from ibrutinib treatment, only a small percentage (7% at one year) achieve complete response and acquired resistance leads to disease progression over time. Combination of VAY736 and ibrutinib has potential to deepen the response to ibrutinib, eliminate the CLL cells with acquired resistance to ibrutinib, and potentially allow for discontinuation of long-term therapy.

[REDACTED]

The purpose of this study is to determine the safe and tolerable dose of VAY736 for use in combination with ibrutinib and explore preliminary efficacy of the combination. After the safe and tolerable dose of VAY736 is determined in dose escalation, two expansion arms will enroll CLL patients currently taking ibrutinib who have either failed to achieve a CR after >1 year of treatment or who have developed a mutation known to confer molecular resistance to ibrutinib and predict relapse. The purpose of the expansion arms is to gather preliminary efficacy data in these specific groups and will test whether addition of VAY736 to ibrutinib can deepen responses and increase the complete response rate.

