5.2 Inclusion criteria

Patients eligible for inclusion in this study have to meet **all** of the following criteria:

Patient must meet the following laboratory values at the screening visit unless cytopenias are related to CLL:

1. Diagnosis of chronic lymphocytic leukemia (CLL) meeting criteria established in the World Health Organization (WHO) classification of hematologic disorders or International Workshop on Chronic Lymphocytic Leukemia (IWCLL) ([Hallek et al 2018](#)). Variant immunophenotype and prolymphocytic morphology change after diagnosis of CLL is allowed.
2. Age \geq 18 years
3. [REDACTED]
4. Male patients agree to avoid fathering a child as per the ibrutinib package insert

5. Dose escalation:
 - a. On ibrutinib > 1 year following relapse from another approved therapy without achieving a complete response

[figure not shown]
OR
 - b. On ibrutinib following relapse with another approved therapy and the presence of a known ibrutinib resistance mutation (BTK or PLC γ 2) at ≥ 1 variant allele frequency OR $< 1\%$ with two separate measurements at least 4 weeks apart with increasing variant allele frequency.
6. Dose expansion:
 - a. Arm A: On ibrutinib > 1 year following relapse from another approved therapy without achieving a complete response and patients who have received ibrutinib either alone or in combination (or have received ibrutinib continuously with multiple sequential combination partners) as first-line therapy and have failed to achieve a complete response after 1 year.
 - b. Arm B: On ibrutinib following relapse with another approved therapy and patients who have received ibrutinib either alone or in combination (or have received ibrutinib continuously with multiple sequential combination partners) as first-line therapy and the presence of a known ibrutinib resistance mutation at $\geq 1\%$ variant allele frequency OR $< 1\%$ with two separate measurements at least 4 weeks apart with increasing variant allele frequency. *Note: As of Amendment 6, patients will no longer be enrolled into Arm B.
7. Ibrutinib dose:
 - Escalation: Patients must be receiving 420 mg ibrutinib
 - Expansion: Patients may be on a dose of ibrutinib lower than 420 mg. Any dose must have been stable for 2 months prior to the start of study treatment.
8. Absolute Neutrophil Count ≥ 750 cells/ μ L ($0.75 \times 10^9/L$) independent of growth factor support within 7 days of the first dose of VAY736

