14.1 Appendix 1 – Guidelines for NCI CLL Working Group 2018 (IWCLL)

This appendix refers to [Hallek et al 2018](#).

Table 14-1 Response definition after treatment for patients with CLL

Group	Parameter	CR	PR	PD	SD
A	Lymph nodes	None ≥ 1.5 cm	Decrease $\geq 50\%$ (from baseline)*	Increase $\geq 50\%$ from baseline or from response	Change of -49% to $+49\%$
	Liver and/or spleen size†	Spleen size < 13 cm; liver size normal	Decrease $\geq 50\%$ (from baseline)	Increase $\geq 50\%$ from baseline or from response	Change of -49% to $+49\%$
	Constitutional symptoms	None	Any	Any	Any
	Circulating lymphocyte count	Normal	Decrease $\geq 50\%$ from baseline	Increase $\geq 50\%$ over baseline	Change of -49% to $+49\%$
B	Platelet count	$\geq 100 \times 10^9/L$	$\geq 100 \times 10^9/L$ or increase $\geq 50\%$ over baseline	Decrease of $\geq 50\%$ from baseline secondary to CLL	Change of -49 to $+49\%$
	Hemoglobin	≥ 11.0 g/dL (untransfused and without erythropoietin)	≥ 11 g/dL or increase $\geq 50\%$ over baseline	Decrease of ≥ 2 g/dL from baseline secondary to CLL	Increase < 11.0 g/dL or $< 50\%$ over baseline, or decrease < 2 g/dL
	Marrow	Normocellular, no CLL cells, no B-lymphoid nodules	Presence of CLL cells, or of B-lymphoid nodules, or not done	Increase of CLL cells by $\geq 50\%$ on successive biopsies	No change in marrow infiltrate

*Sum of the products of 6 or fewer lymph nodes (as evaluated by CT scans and physical examination in clinical trials or by physical examination in general practice).

†Spleen size is considered normal if < 13 cm. There is not firmly established international consensus of the size of a normal liver; therefore, liver size should be evaluated by imaging and manual palpation in clinical trials and be recorded according to the definition used in a study protocol.

CR, complete remission (all of the criteria have to be met); PD, progressive disease (at least 1 of the criteria of group A or group B has to be met); PR, partial remission (for a PR, at least 2 of the parameters of group A and 1 parameter of group B need to improve if previously abnormal; if only 1 parameter of both groups A and B is abnormal before therapy, only 1 needs to improve); SD, stable disease (all of the criteria have to be met; constitutional symptoms alone do not define PD).

Table 14-2 Grading scale for hematologic toxicity in CLL studies

Grade*	Decrease in platelets [†] or Hb [‡] (nadir) from pretreatment value, %	Absolute neutrophil count/ μ L [§] (nadir)

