5.2.2.3.2 Overall disease response criteria

The general principle of overall disease response determination at a given evaluation is described in [Table 5-1](#). Also refer to [Hallek et al 2018](#) for a detailed explanation of each response criteria.

Table 5-1 Overall disease response classification at a given evaluation time

Response category	Definition
Complete remission (CR)	All the following criteria in Group A and Group B must be met and patients don't have disease-related constitutional symptoms:
	Group A
	Lymphadenopathy
	
None \geq 1.5 cm (CT is required at time of establishing CR/CRI if abnormal at baseline)
	Hepatomegaly
	
Liver size normal (CT is required at time of establishing CR/CRI if abnormal at baseline)
	Splenomegaly
	
Spleen size normal (CT is required at time of establishing CR/CRI if abnormal at baseline)
	Blood lymphocytes

Response category	Definition
	
• < 4000 /μL
Group B	
	Platelet count
	
• \geq 100,000 /μL
	Hemoglobin
	
• \geq 11.0 g/dL (without red blood cell transfusions or erythropoietin support within 7 days)
	Neutrophils
	
• \geq 1500 /μL
	Marrow
	
• Normocellular, no CLL cells, no B-lymphoid nodules
Complete remission with incomplete marrow recovery (CRi)	All criteria for CR as defined above are met, except a persistent anemia or thrombocytopenia or neutropenia apparently unrelated to CLL.
Partial remission (PR)	At least two of the criteria of Group A plus one of the criteria of Group B below must be met if abnormal at baseline. If only one parameter of both groups A and B is abnormal prior to therapy, only 1 needs to improve.
	Group A
	Lymphadenopathy
	
• Decrease \geq 50% from baseline (CT is required at time of establishing PR if abnormal at baseline) or meet CR criteria.
	Hepatomegaly
	
• Decrease \geq 50% from baseline of enlargement of liver below the costal margin by physical exam or meet CR criteria.
	Splenomegaly
	
• Decrease \geq 50% from baseline of enlargement of spleen below the costal margin by physical exam or meet CR criteria.
	Blood lymphocytes
	
• Decrease \geq 50% from baseline or meet CR criteria.
Group B	

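### The C9 CR/CRi rate ignores remission status at baseline, so an Arm B patient who enters in CR or CRi on ibrutinib alone would count as a response

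*SAP*

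**What the plan says.** On the endpoint, SAP 2.8.1 says: "The rate of CR/CRi at C9 is the primary endpoint for the evaluation of anti-tumor activity and will be analyzed for each expansion arm". The numerator is "The proportion of patients with CR or CRi assessed by investigators per IWCLL criteria" at C9, and the set is the FAS: "Analyses of these variables will use the FAS, including patients from both the escalation and expansion parts". Neither 2.8.1 nor the missing-data rule in 2.6.2 mentions remission status at baseline. The CR criteria in Protocol Table 14-1 and SAP Table 5-1 are fixed thresholds, not changes from baseline, so a remission that is merely maintained meets them.

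On purpose, Protocol 2.1 says the expansion arms "will test whether addition of VAY736 to ibrutinib can deepen responses and increase the complete response rate".

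On entry, the Protocol summary gives two alternatives: "Lack of a complete response after receiving ibrutinib for > 1 year OR presence of known ibrutinib resistance mutation". Protocol 5.2 applies the first to Arm A in criterion 6a, "Arm A: On ibrutinib > 1 year following relapse from another approved therapy without achieving a complete response", with a matching condition for first-line patients. Arm B (6b) and escalation route 5b use the second alternative. They ask for a resistance mutation and set no condition on remission.

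On CRi, SAP Table 5-1 defines it as: "All criteria for CR as defined above are met, except a persistent anemia or thrombocytopenia or neutropenia apparently unrelated to CLL". SAP section 4 records that the protocol's appendix has only CR, PR, SD and PD, and that the SAP added CRi. The eligibility text still refers only to complete response.

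**The concern.** The efficacy question is whether adding VAY736 produces remissions that ibrutinib had not. A patient already in remission cannot answer it, yet the rule as written scores that patient as a success if the remission holds to C9. A carried-over remission can only add to the numerator, and there is no control arm in which the same carry-over would show.

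What is at stake is the reading of the posterior. The SAP sorts the rate into not meaningful, moderate and superior benefit, and with about 20 patients planned per arm each responder is worth 1/20 = 5 percentage points.

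**Working it through.** **Step 1. Entry route against endpoint.**

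| Route | Entry condition | CR at entry | CRi at entry | Enters the Bayesian posterior? |
|---|---|---|---|---|
| Arm B, 6b | resistance mutation | not barred | not barred | yes |
| Escalation, 5b | resistance mutation | not barred | not barred | no, by-dose summaries only |
| Arm A, 6a | no CR on ibrutinib | barred | unclear | yes |
| Escalation, 5a | no CR on ibrutinib | barred | unclear | no, by-dose summaries only |

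Protocol 4.1 describes Arm B patients as not yet in clinical relapse, which is compatible with CR. In expansion, all mutation carriers go to Arm B.

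Two other provisions might seem to close the gap. Exclusion criterion 4 mentions measurable disease, but only within the radiotherapy exclusion. SAP 5.2.2.1.1 accepts patients with no measurable nodes at baseline. Neither bars a patient in remission from Arm B.

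**Step 2. Reproduce the SAP's figures.** Inputs: prior Beta(0.25, 1) from SAP 2.8.1, N = 20 and the cut-points 20% and 40%. With x responders the posterior is Beta(0.25 + x, 1 + N − x), with mean (0.25 + x)/(1.25 + N). For 6/20 this is Beta(6.25, 15): mean 6.25/21.25 = 0.294, P(<20%) = 0.170, P(≥40%) = 0.143. All five rows of SAP Table 3-2 reproduce to three decimals.

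**Step 3. Sensitivity to baseline remissions.** The documents do not give k, the number of responders already in CR/CRi at baseline; k = 1 and 2 are assumptions. Start from 6/20 and remove k from numerator and denominator:

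| k | x/N | Posterior | Mean | P(<20%) | P(≥40%) |
|---|---|---|---|---|---|
| 0 | 6/20 | Beta(6.25, 15) | 0.294 | 0.170 | 0.143 |
| 1 | 5/19 | Beta(5.25, 15) | 0.259 | 0.290 | 0.082 |
| 2 | 4/18 | Beta(4.25, 15) | 0.221 | 0.453 | 0.040 |

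**Step 4. A smaller arm.** Arm B closed to enrolment at Amendment 6 because enrolment was slow, so N = 20 may overstate its size. At an assumed N of 10, one baseline remission among 3/10 responders leaves 2/9, and P(<20%) moves from 0.274 to 0.497.

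**The case against.** The best case on the other side has five parts.

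- **Arm A excludes CR.** A reader might infer that the trial as a whole admits patients in CR. It does not: 6a and 5a both require that CR was not reached, and Arm A is the only expansion arm enrolling after Amendment 6. This stands.
- **CRi in Arm A is an ambiguity.** A reader might infer that CRi patients plainly qualify. But Protocol 4.1 and SAP 2.1 describe Arm A as patients with residual disease, which a patient in CRi does not plainly fit. The Protocol's account of the randomised ibrutinib versus chlorambucil trial also counts incomplete blood-count recovery among complete responses, so the eligibility term may already cover CRi. This stands as a reason for uncertainty.
- **Never-biopsied patients.** PR in Table 14-1 allows marrow "Presence of CLL cells, or of B-lymphoid nodules, or not done", so a reader might infer that an undocumented CR could enter Arm A and first be shown at C9. SAP 5.2.2.2 makes marrow mandatory at baseline, which undercuts this, and the protocol's disease-assessment plan is partly redacted. The documents do not support that reading.
- **Arm B entry is deliberate.** The arm has its own endpoint, clearance of the mutation, for which remission status need not matter. That defends the entry rule. It does not defend scoring a pre-existing remission as a C9 response.
- **Context is reported elsewhere.** SAP 2.3.4.1 summarises best response to the last prior treatment, and 2.3.5 summarises stage at entry. Neither is a baseline remission flag, and neither is linked to C9. The supportive analyses in SAP 2.6.3 are partly redacted and cannot be judged.

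**Conclusion.** The point holds for Arm B, where the rule as written would count a CR or CRi that preceded VAY736. It holds for escalation route 5b in the descriptive summaries only. In Arm A it is limited to a possible baseline CRi.

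A reader might go further and infer that the reported rate is inflated. The documents do not show that any patient entered in CR or CRi, and the number may be zero. The shift in P(clinically not meaningful) from 0.170 to 0.290 or 0.453 shows how sensitive the posterior is to assumed counts of 1 or 2 at N = 20. It does not estimate actual bias.

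Severity is moderate. The endpoint is secondary and concerns preliminary activity in a Phase Ib trial. There is no formal power calculation, and the unredacted text ties no decision rule to the posterior.

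**What to change.** Change the SAP only. Rewording eligibility would not alter who has already been enrolled, and SAP section 1 records that early termination has been endorsed.

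1. Derive IWCLL status at baseline from the blood, CT, marrow and symptom assessments that SAP 5.2.2.2 already makes mandatory, using the CR and CRi definitions in Table 5-1.
2. Tabulate that status by arm, and by dose level in escalation, with Unknown as its own row.
3. Base the C9 CR/CRi posterior summaries on patients not in CR/CRi at baseline. List baseline CR/CRi patients separately with their C9 status, and show the all-FAS rate alongside.

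Keeping baseline remissions in the denominator as non-responders is a harsher alternative: 5/20 and 4/20 give P(<20%) of 0.332 and 0.544, against 0.290 and 0.453 above. It scores as failures patients who had no remission left to gain, so it is not the version proposed here.

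The cost is one derived variable, one table and one listing from data the SAP already requires, plus a slightly smaller denominator if any such patients exist. If there are none, the result is unchanged.
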